## **Statistical Analysis**

The primary outcome variables are PD reduction, RAL gain, and reduction in BOP. PD data was computed to provide a mean score per mouth. Secondary efficacy variables were BOP, and MQH. BOP was computed to provide a mean score per mouth for each clinical assessment and were analyzed using repeated measures (ANOVA). Outcome variable data analysis consisted of between-treatment and within-treatment (longitudinal) comparisons of PD and CAL at all examination time points using parametric procedures. Between-treatment and within-treatment comparisons employed baseline data and analysis of covariance (ANCOVA) for follow-up data. All comparisons were performed using two-sided hypothesis tests, and employed a 0.05 level of significance.

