## ABSTRACT OF THE THESIS

Custom Application of Peroxide Gel as Adjunct to Scaling/Root planning in Treatment of Periodontitis

by

[name]

Master of Science, Graduate Program in Periodontics

Loma Linda University, September 2019

[name] [name], Chairperson

**Aim:** This study was aimed to evaluate and compare the clinical effects of scaling and root planning (SRP) combined with local delivery of 1.7% HP in customized trays to that of SRP alone.

**Materials and Methods:** Sixty patients with generalized moderate to chronic severe periodontitis will be assigned to three groups treated by SRP plus HP gel with a custom prescription tray application. The test groups will receive twice daily 1.7% HP gel in custom trays four weeks prior to SRP and will continue to application for up to 3- and 6-months post-SRP. Baseline data that is collected at the start of the study will be collected again at 4, 13, and 26 weeks post-SRP and analyzed for any changes and thus main outcome variables will include changes in pocket depth (PD), relative recession (R-Rec), relative attachment level (RAL), and changes in bleeding (BOP) using ANCOVA of main effects.

**Results:** Repeated measure ANOVA showed significant difference in pocket depth among all time points in all treatment groups. Mean BOP was significantly reduced in all groups between 4-week examination and re-evaluation with mean BOP scores at final

examination staying similar to levels at re-evaluation for HP13 and HP26 groups. Mean BOP scores at final examination group for SRP group was similar to baseline.

**Discussion:** The use of adjunctive HP in custom fabricated trays presents with no adverse effects. Significant improvement was evident in pocket depth and attachment level in both treatment groups between after 4 weeks of using the tray. No significant effect found in SRP group between baseline and 4 weeks. After SRP, significant difference was seen in all three groups between 4 weeks and 3 months.

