## CHAPTER THREE

### RESULTS

There were total 15 subjects who completed the 6-month trial. There were 10 males with an mean age of 55.6 years and 8 males with an mean age of 51.1 years. There was a total of 3 patients in SRP group, 3 patients in HP13 group, and 9 patients in HP26 group. The mean pocket depth (PD) shown in figure 1 at baseline for SRP group was  $3.88 \pm 0.06$  mm (std. error),  $4.11 \pm 0.06$  mm for HP13, and  $3.83 \pm 0.04$  mm for HP26. At the 4-week examination, PD for SRP group decreased to  $3.67 \pm 0.06$  mm,  $4.06 \pm 0.06$  mm with HP13, and  $3.55 \pm 0.04$  mm for HP26. At the re-evaluation examination, PD for SRP group was  $3.30 \pm 0.06$  mm,  $3.43 \pm 0.06$  mm for HP13, and  $3.14 \pm 0.04$  mm for HP26. The final examination, PD were  $3.43 \pm 0.06$  for SRP,  $3.40 \pm 0.06$  mm for HP 13, and  $3.23 \pm 0.04$  mm for HP26. Repeated measure ANOVA showed significant difference in pocket depth among all time points in all treatment groups. In SRP group, no significant difference between baseline and 4 weeks in pocket depth and relative attachment level.

[figure not shown]

Figure 2. Mean PD in each group, SRP, HP13, and HP26.

Figure 2 shows the mean relative recession over time. The mean relative recession at baseline was  $3.28 \pm 0.06$  mm for SRP,  $2.87 \pm 0.06$  mm for HP13, and  $3.21 \pm 0.03$  mm for HP13. At 4-weeks, it was  $3.35 \pm 0.06$  mm for SRP,  $3.23 \pm 0.05$  mm for HP13, and  $3.15 \pm 0.03$  mm for HP26. At re-evaluation it was  $3.33 \pm 0.06$  mm for SRP,  $3.27 \pm 0.05$  mm for HP13, and  $3.29 \pm 0.03$  mm for HP26.

[figure not shown]

Figure 3. Mean R-Rec in each group, SRP, HP13, and HP26.

Figure 3 shows the mean relative attachment level. The mean RAL at baseline was  $7.16 \pm 0.08$  mm for SRP,  $6.97 \pm 0.07$  mm for HP13, and  $7.04 \pm 0.04$  mm for HP26. At 4-weeks, the RAL was  $7.02 \pm 0.08$  mm for SRP,  $7.29 \pm 0.07$  mm for HP13, and  $6.69 \pm 0.05$  mm for HP26. At re-evaluation the RAL was  $6.63 \pm 0.08$  mm for SRP,  $6.15 \pm 0.07$  mm for HP13, and  $6.39 \pm 0.04$  mm for HP26. At the final exam RAL was  $6.79 \pm 0.08$  mm for SRP,  $6.71 \pm 0.07$  mm for HP13, and  $6.53 \pm 0.04$  mm for HP26.

[figure not shown]

Figure 4. Mean RAL in each group, SRP, HP13, and HP26.

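### The analysis plan tests no recession outcome and assigns attachment to an unmeasured CAL, so the recession conclusion rests on no reported test, and it and the week-4 attachment conclusion conflict with the printed HP13 means

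*Combined protocol and SAP*

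**What the plan says.** In the Combined protocol and SAP, Chapter Two, Statistical Analysis:

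- Primary: "The primary outcome variables are PD reduction, RAL gain, and reduction in BOP".
- Secondary: "Secondary efficacy variables were BOP, and MQH".
- Analysed: "comparisons of PD and CAL at all examination time points using parametric procedures".
- Model: the comparisons "employed baseline data and analysis of covariance (ANCOVA) for follow-up data".

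R-Rec appears in none of these. CAL is absent from the Abbreviations list and from the measurements under Clinical Periodontal Parameters. A per-mouth mean is defined for PD and BOP, but not for RAL.

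The Abstract says that "main outcome variables will include changes in pocket depth (PD), relative recession (R-Rec), relative attachment level (RAL), and changes in bleeding (BOP", with ANCOVA as the method. Clinical Periodontal Parameters defines three distances: R-Rec from stent margin to gingival margin, PD from gingival margin to pocket base, and RAL from stent margin to pocket base. Chapter One sets separate null hypotheses for PD, attachment and BOP, and no section says how they combine.

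In Chapter Three, the sentence "Figure 2 shows the mean relative recession over time" introduces R-Rec means at baseline, week 4 and re-evaluation. The text gives no final R-Rec, although it gives final PD and RAL. Chapter Four then concludes that recession did not rise with tray use. Chapter Five reports significantly better pocket depth and attachment in both peroxide arms after four weeks.

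**The concern.** By the trial's own definitions a pocket becomes shallower either because attachment is gained or because the gingival margin recedes. PD alone cannot tell these apart. Recession also matters in its own right, because the tray seals at the gingival margin and the Discussion draws a conclusion about exactly that.

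A conclusion on recession needs a planned comparison with an interval, and the Statistical Analysis section provides none. The attachment comparison is planned under a name that matches no measured variable. At stake are two published statements: that trays do not promote recession, and that four weeks of tray use before SRP improved attachment in both peroxide arms.

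**Working it through.** **Inputs.** Printed means in mm from Chapter Three. The baseline R-Rec of 3.21 carries the HP13 label a second time and is read here as HP26. Completers: SRP 3, HP13 3, HP26 9. The plan contains no figure of its own to reproduce on this point.

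**Step 1. Do the printed means fit the definitions?** The definitions imply RAL = PD + R-Rec.

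| Arm, visit | PD | R-Rec | Sum | RAL printed | Gap |
|---|---|---|---|---|---|
| SRP, baseline | 3.88 | 3.28 | 7.16 | 7.16 | 0.00 |
| SRP, week 4 | 3.67 | 3.35 | 7.02 | 7.02 | 0.00 |
| SRP, week 13 | 3.30 | 3.33 | 6.63 | 6.63 | 0.00 |
| HP13, baseline | 4.11 | 2.87 | 6.98 | 6.97 | 0.01 |
| HP13, week 4 | 4.06 | 3.23 | 7.29 | 7.29 | 0.00 |
| HP13, week 13 | 3.43 | 3.27 | 6.70 | 6.15 | 0.55 |
| HP26, baseline | 3.83 | 3.21 | 7.04 | 7.04 | 0.00 |
| HP26, week 4 | 3.55 | 3.15 | 6.70 | 6.69 | 0.01 |
| HP26, week 13 | 3.14 | 3.29 | 6.43 | 6.39 | 0.04 |

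Eight of nine agree within 0.04 mm. The HP13 re-evaluation row does not, so at least one of its three values needs checking.

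**Step 2. Recession against the Discussion.** Change in R-Rec, baseline to week 13 (a rise is recession):

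- SRP: 3.33 − 3.28 = +0.05
- HP13: 3.27 − 2.87 = +0.40
- HP26: 3.29 − 3.21 = +0.08

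The HP13 week-13 value sits in the row that fails Step 1. If R-Rec were the wrong entry there, it would be 6.15 − 3.43 = 2.72, a change of −0.15. The rise does not depend on that visit alone: at week 4 it is already 3.23 − 2.87 = +0.36, in a row that fits exactly.

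**Step 3. Week-4 attachment against the Conclusion.** HP13 RAL changes by 7.29 − 6.97 = +0.32, which is a worsening. PD falls by 0.05 and R-Rec rises by 0.36 over the same interval. HP26 RAL improves by 7.04 − 6.69 = 0.35. The printed means therefore show better attachment in one peroxide arm, not both.

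**Step 4. The final visit, derived.** R-Rec = RAL − PD:

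- SRP: 6.79 − 3.43 = 3.36 (+0.08 from baseline)
- HP13: 6.71 − 3.40 = 3.31 (+0.44)
- HP26: 6.53 − 3.23 = 3.30 (+0.09)

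These rest on the identity that fails once in Step 1. A printed final value may exist in the R-Rec figure, which was not available.

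**Step 5. HP13 against SRP at week 26.** As change from baseline, PD reduction is 0.71 against 0.45 (HP13 better by 0.26) and RAL gain is 0.26 against 0.37 (HP13 worse by 0.11). The plan specifies ANCOVA, for which the adjusted difference is the final difference minus b times the baseline difference. No slope b is reported, so take 0 to 1:

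- PD: (3.40 − 3.43) − b(4.11 − 3.88) = −0.03 − 0.23b, from −0.03 to −0.26.
- RAL: (6.71 − 6.79) − b(6.97 − 7.16) = −0.08 + 0.19b, from −0.08 (HP13 better) to +0.11 (HP13 worse), with the sign changing at b = 0.08/0.19 = 0.42.

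**The case against.** The best answer is that RAL gain is itself primary. RAL is read from a fixed stent, so a receding margin cannot inflate it, and attachment has its own null hypothesis. R-Rec equals RAL minus PD, so the information is already in the data. CAL is most plausibly a slip for RAL. R-Rec is also defined, scheduled at baseline, partly reported and discussed, so it has not vanished from the trial. The final value may be in the unavailable figure.

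Most of this stands, and it limits the point. The plan does not leave recession uncontrolled, and the Abstract and the Statistical Analysis section are in conflict rather than silent. It does not supply a test, though: subtracting printed means gives no adjusted contrast and no interval for the statement made in the Discussion.

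A reader might go further and infer that HP13 beats SRP on PD only through recession, since 0.44 of its 0.71 mm PD reduction (62%) is implied recession. The documents do not support that. It rests on raw changes in 3 against 3 completers with unequal baselines, final PD is nearly equal, and the direction on RAL under the planned ANCOVA depends on an unreported slope. HP26, the larger arm, exceeds SRP on both measures (0.60 − 0.45 = 0.15 on PD, 0.51 − 0.37 = 0.14 on RAL). The text does not claim that HP13 beats SRP on PD.

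A reader might also want PD claims barred whenever RAL points the other way. Chapter One names PD reduction as a benefit in its own right, and such a rule without a margin or interval would turn on noise at these numbers.

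**Conclusion.** The point holds in limited form. The Statistical Analysis section plans no test of recession, contradicts the Abstract on whether R-Rec is an outcome, and assigns the attachment comparison to a variable that is not measured. PD can therefore be read without its recession component beside it.

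Two conclusions do not match the printed means: no increase in recession with trays (HP13 +0.36 mm at week 4 and +0.40 mm at week 13), and better attachment in both peroxide arms at week 4 (HP13 worse by 0.32 mm).

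This assumes that the printed means are correct apart from the flagged HP13 re-evaluation row, and that the baseline 3.21 belongs to HP26. With 3, 3 and 9 completers the figures show that the wording and the numbers disagree. They do not establish that trays cause recession.

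**What to change.** 1. In Statistical Analysis, replace CAL with RAL and state its per-mouth summary, as is done for PD and BOP.
2. Add R-Rec as an analysed outcome with the same baseline-adjusted ANCOVA at weeks 4, 13 and 26, so that the section agrees with the Abstract. The SRP visit list does not mention stent measurements at week 4, although Results prints week-4 SRP means; reconcile these as well.
3. In Results, give the final R-Rec and show the PD, RAL and R-Rec contrasts side by side with confidence intervals.
4. Check the HP13 re-evaluation row against source data (RAL 6.15 printed, 6.70 from PD plus R-Rec) and the duplicated HP13 label on the baseline R-Rec of 3.21.
5. Restate the recession sentence in the Discussion and the week-4 attachment sentence in the Conclusion (and in the Abstract, which repeats it) to match the corrected results.

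The cost is wording and one more model on data already collected. With 15 completers, three arm means and one slope leave 15 − 4 = 11 residual degrees of freedom at each visit, so precision will be limited. The recession and attachment statements will become less favourable.

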### **Clinical Periodontal Parameters**

When collecting data, the examiner was blinded to treatment groups. Using the same PVS (Exafast™ NDS, GC America, Alsip IL) impressions to fabricate stone models

(Microstone, Whipmix Corp., Louisville, KY) a customized stent was fabricated using a positive pressure thermoplastic mold device (Biostar® Scan/Biostar® V, Great Lakes Orthodontics, New York). This 1-mm thick, semi-rigid stent was used as reference for the linear measurements using a periodontal probe (15 UNC Color-Coded Probe, Hu-Friedy, Chicago IL). All the measurement will be at 1 mm increments. Clinical parameter measurements was taken at six sites (mesio-buccal, mid-buccal, disto-buccal, mesio-lingual, mid-lingual, and disto-lingual) of each tooth. Relative gingival recession (R-REC) was measured from a margin of the stent to the most coronal height of the gingival margin. PD was measured as the distance from the gingival margin to the depth of the pocket. The probe was held flat against the tooth near the gingival margin and inserted into the periodontal pocket in a path that is parallel to the long axis of the tooth and advanced using light pressure until slight resistance is felt. Relative attachment level (RAL) was measured from a margin of the stent to the bottom of the pocket.

Bleeding on probing (BOP) was measured with sites that show any bleeding within 30 seconds of probing and was recorded as a percentage.

Oral hygiene level was measured by using the Modified Quigley-Hein Plaque Index (MQH) with disclosing solution that measures plaque on all teeth except 3rd molars at 4 surfaces on the buccal and lingual surfaces where:

Score 0 has no plaque

Score 1 has separate flecks of plaque along the cervical margin of the tooth

Score 2 has a  $\leq 1$  mm band of plaque at the cervical margin of the tooth

Score 3 has a band of plaque  $> 1$  mm but  $< \frac{1}{3}$  of the crown of the tooth

Score 4 has plaque that is covering  $\geq \frac{1}{3}$  but  $< \frac{2}{3}$  of the crown of the tooth.

Score 5 has plaque covering  $\geq \frac{2}{3}$  of the crown of the tooth

Full mouth series of periapical and bitewing radiographs was captured for all patients for standard periodontal diagnostic procedure as a part of the comprehensive periodontal evaluation. Radiographs of patients that were referred other clinics taken within a year of the comprehensive periodontal evaluation was used.

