### **Randomization; Sequence, Allocation, and Implementation**

Subjects were assigned randomized identification (ID) numbers during enrollment (Visit 1), which will be recorded on all Case Report Forms (CRF) and the Product Accountability Log. Immediately following the preliminary clinical parameter recording the investigators randomly allocated subjects in a group using a predetermined random group assigner (SAS, SAS Institute, Cary NC) based upon subjects' ID numbers. Each subject received non-surgical periodontal therapy (SRP) as indicated in areas with increased probing depths.

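### The plan states no unit of analysis for attachment level, and the printed errors for RAL, R-Rec and PD all look too small to be patient-level errors

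*Combined protocol and SAP*

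**What the plan says.** The Statistical Analysis section of Chapter Two lists three primary variables: "The primary outcome variables are PD reduction, RAL gain, and reduction in BOP". It fixes the unit of analysis for two of them. For pocket depth, "PD data was computed to provide a mean score per mouth"; for bleeding, "BOP was computed to provide a mean score per mouth for each clinical assessment". Attachment level appears only in the general sentence on "comparisons of PD and CAL at all examination time points using parametric procedures", followed by ANCOVA for follow-up data. That sentence uses CAL, which is not in the Abbreviations list. No per-mouth mean, patient effect or other handling of clustering is stated for attachment level or for R-Rec.

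Under Clinical Periodontal Parameters, "Clinical parameter measurements was taken at six sites (mesio-buccal, mid-buccal, disto-buccal, mesio-lingual, mid-lingual, and disto-lingual) of each tooth", in 1 mm steps. Eligibility requires at least 20 teeth. The Randomization section makes the patient the unit of allocation: "the investigators randomly allocated subjects in a group using a predetermined random group assigner".

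Results reports 15 completers (SRP 3, HP13 3, HP26 9) and gives PD, R-Rec and RAL as a mean with an error. Only the first PD value is labelled as a standard error.

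**The concern.** Each patient supplies at least 20 × 6 = 120 readings that share one mouth, one stent and one disease history. If these are analysed as independent, chance differences between patients are read as treatment effects, and enrolling all 60 planned patients would not help. Because the plan is silent on the unit for attachment level, a site-level test would comply with it.

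The errors in Results sharpen the question. They are very small for arms of 3, 3 and 9 patients, and this is equally so for PD, the outcome for which the plan does set a per-mouth mean. At stake are the null hypothesis on attachment gain and the significance statements on PD and attachment in the Abstract, Results and Conclusion.

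**Working it through.** The documents give no SD, ICC or sample-size calculation, so there is no planned figure to reproduce. The printed errors can only be worked backwards. I assume that all of them are standard errors and that the third baseline R-Rec value, printed under HP13, belongs to HP26.

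**1. Implied SDs at baseline.** If the patient is the unit, SD = SE × √n. If sites are counted as independent, SD = SE × √(n × m), with m = 120 (20 teeth) or 168 (28 teeth, assumed).

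| Measure, arm | SE (mm) | n | Between-patient SD | Site SD, m = 120 | Site SD, m = 168 |
|---|---|---|---|---|---|
| RAL, SRP | 0.08 | 3 | 0.14 | 1.52 | 1.80 |
| RAL, HP13 | 0.07 | 3 | 0.12 | 1.33 | 1.57 |
| RAL, HP26 | 0.04 | 9 | 0.12 | 1.31 | 1.56 |
| R-Rec, SRP and HP13 | 0.06 | 3 | 0.10 | 1.14 | 1.35 |
| R-Rec, HP26 | 0.03 | 9 | 0.09 | 0.99 | 1.17 |
| PD, SRP and HP13 | 0.06 | 3 | 0.10 | 1.14 | 1.35 |
| PD, HP26 | 0.04 | 9 | 0.12 | 1.31 | 1.56 |

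A between-patient SD of 0.09 to 0.14 mm is about a tenth of one probe step, in patients whose disease runs from moderate to severe. A site SD of about 1.0 to 1.8 mm is plausible for single readings in 1 mm steps. Only the size of the errors discriminates: the ratio between arms of 9 and 3 is near √3 under either unit.

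**2. Baseline differences between arms.** With weights w = 1/SE², Q = Σw(mean − weighted mean)² on 2 df, and p = exp(−Q/2).

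- R-Rec ("The mean relative recession at baseline was" 3.28, 2.87 and 3.21 mm): the weighted mean is 3.165 and Q = 3.67 + 24.17 + 2.25 = 30.1, p = 3 × 10⁻⁷. As F on 2 and 12 df, Q/2 = 15.05, p = 0.0005.
- PD (3.88, 4.11, 3.83): Q = 15.35, p = 0.0005. As F, 7.68, p = 0.007.
- RAL (7.16, 6.97, 7.04): Q = 3.23, p = 0.20.

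On the printed errors, two of the three measures separate the arms before any treatment. RAL does not.

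**3. A check on RAL itself.** The two peroxide arms are treated alike until week 13. At week 4 their RAL is 7.29 ± 0.07 (HP13) and 6.69 ± 0.05 (HP26): z = 0.60/√(0.07² + 0.05²) = 0.60/0.086 = 7.0. The 7.29 is not an obvious misprint, since it equals the printed R-Rec plus PD (3.23 + 4.06).

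**4. False-positive rate if sites were the unit.** The design effect is D = 1 + (m − 1) × ICC. For a large-sample three-arm test (2 df), the actual level is 0.05^(1/D). The ICC is assumed.

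| ICC | D, m = 120 | Actual level | D, m = 168 | Actual level |
|---|---|---|---|---|
| 0.01 | 2.19 | 25% | 2.67 | 33% |
| 0.05 | 6.95 | 65% | 9.35 | 73% |
| 0.10 | 12.9 | 79% | 17.7 | 84% |

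Simulation at m = 120 (20,000 trials per setting) agrees: 25%, 65% and 80% with 3/3/9 patients and 26%, 66% and 79% with 20 per arm. ANOVA on patient means stays near 5%.

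**5. Illustration.** "At the final exam RAL was" 6.79 ± 0.08 mm for SRP and 6.53 ± 0.04 mm for HP26. The printed errors give z = 0.26/√(0.08² + 0.04²) = 0.26/0.0894 = 2.91, p = 0.004. If they are site-level errors and are multiplied by √D (m = 120), p becomes 0.049, 0.27 and 0.42 at ICC 0.01, 0.05 and 0.10.

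**6. Evidence the other way.** The SRP fall in PD from 3.88 to 3.67 mm at 4 weeks is reported as not significant. The printed errors give z = 0.21/√(0.06² + 0.06²) = 2.47, unpaired p = 0.013.

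**The case against.** A reader might infer that PD was tested per patient and RAL per site, and that the reported attachment findings carry error rates of 65% to 80%. The documents do not support either step.

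- **PD and RAL look alike.** The PD errors are as small as the RAL errors despite the per-mouth rule, so they do not show that RAL was handled differently. This stands, and it widens the recomputation to PD.
- **The text is silent on attachment, not wrong.** It does not describe the model terms. PD and CAL share one sentence, so reading both as per-mouth is natural. This stands, but a primary outcome should not depend on that reading.
- **The baseline check is mixed.** RAL is homogeneous at baseline, and 15 completers out of 60 planned patients need not be balanced as randomised. Both points stand. Neither explains between-patient SDs near 0.1 mm or the week-4 gap between two arms treated alike.
- **The tests may not have used the printed errors.** The SRP result in step 6 points that way. A multiplicity adjustment, which the plan does not mention, could also explain it: Bonferroni over the six pairs of four visits gives 6 × 0.013 = 0.08. The unit cannot be settled from the documents.
- **The rates are for between-arm tests.** No significant between-arm RAL result is reported; the attachment statements concern change within groups. Stable patient differences then cancel, and the ICC of the site changes applies, which is not given. This stands.
- **One attachment claim fails on other grounds.** The Conclusion reports improved attachment in both peroxide groups at 4 weeks, but HP13 RAL rose from 6.97 to 7.29 mm. This is true whatever the unit.

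**Conclusion.** The concern holds in this form. The plan leaves the unit of analysis for a primary outcome unstated, and the errors printed for RAL, R-Rec and PD are implausible as patient-level errors for 3, 3 and 9 patients. That follows from the implied between-patient SDs of 0.09 to 0.14 mm, supported by the pre-treatment differences in R-Rec and PD and the week-4 gap in RAL. More than missing detail is involved, because the published error bars themselves need correcting.

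The errors fit site-level counting but do not establish which unit the tests used. The between-arm false-positive rates of about 25%, 65% and 80% are conditional on a site-level test and on assumed ICCs of 0.01, 0.05 and 0.10. They are not error rates of the within-group claims made. The conclusion also assumes that the unlabelled errors are standard errors and that mouths have 120 to 168 sites. Confidence is high on the gap in the plan and moderate on the cause of the small errors.

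**What to change.** **In Statistical Analysis:** state that PD, RAL and R-Rec are each averaged to one value per patient per visit and analysed with one row per patient. The alternative is a site-level mixed model with random effects for patient and tooth and small-sample degrees of freedom. Replace CAL with RAL.

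**In Results:** say what the errors are, and recompute errors and tests for all three measures with the patient as the unit (n = 3, 3 and 9). Withdraw any PD or attachment significance statement in the Abstract, Results or Conclusion that does not survive.

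**Cost:** a sentence or two and a re-run on data already held. Intervals will widen, some significance statements will probably be lost, and tests on 3, 3 and 9 patients will have little power.

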Figures 4, 5, 6, and 7 show baseline, 4-week, re-evaluation, and final MQH plaque scores. Plaque scores varied throughout the four timepoints with no obvious differences between groups.

[figure not shown]

Figure 5. Baseline MQH scores for A) SRP, B) HP13, and C) HP26

[figure not shown]

Figure 6. 4-Week MQH scores for A) SRP, B) HP13, and C) HP26.

[figure not shown]

Figure 7. Re-Evaluation MQH scores for A) SRP, B) HP13, and C) HP26.

[figure not shown]

Figure 8. Final MQH scores for A) SRP, B) HP13, and C) HP26.

[figure not shown]

Figure 9. Mean BOP in each group, SRP, HP13, and HP26

[figure not shown]

Figure 10. BOP % in pockets initially <5 mm

[figure not shown]

Figure 11. BOP % in pockets initially  $\geq 5$ mm

Figure 8 shows mean BOP. Baseline mean BOP was 45% for SRP, 57% for HP13, and 63.1% for HP26. At 4-weeks, mean BOP was 45% for SRP, 60% for HP13, and 44% for HP26. At re-evaluation, mean BOP was 37% for SRP, 30% for HP13, and 27% for HP26. Final mean BOP scores were 44% for SRP, 33% for HP13, and 28% for HP13. Mean BOP was significantly reduced in all groups between 4-week examination and re-evaluation with mean BOP scores at final examination staying similar to levels at re-evaluation for HP13 and HP26 groups. Mean BOP scores at final examination group for SRP group was similar to baseline.

Figure 9 shows BOP % in pockets initially  $< 5$ mm. At baseline, 24% of pockets  $< 5$ mm were BOP for SRP, 47% for HP13, and 52% for HP26. At 4-week examination BOP % were 29% for SRP, 44% for HP13, and 35% for HP26. At re-evaluation, BOP %

was 27% for SRP, 21% for HP13, and 22% for HP26. At the final exam, BOP % was 33% for SRP, 26% for HP13, and 22% for HP26.

Figure 10 shows BOP % in pockets initially  $\geq 5$ mm. At baseline, BOP % was 92% for SRP, 81% for HP13, and 91% for HP26. At 4-week examination, BOP % was 91% for SRP, 93% for HP13, and 83% for HP26. Re-evaluation BOP % was 91% for SRP, 78% for HP13, and 75% for HP26. At final examination, BOP % was 88% for SRP, 79% for HP13, and 78% for HP26.

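### BOP has no single named between-arm analysis, and the readable results do not support the Discussion's significance claim as a benefit over SRP alone

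*Combined protocol and SAP*

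**What the plan says.** **Statistical Analysis (Chapter Two).** One paragraph contains all of the following.
- The role of BOP: "The primary outcome variables are PD reduction, RAL gain, and reduction in BOP". Two sentences later: "Secondary efficacy variables were BOP, and MQH".
- The method for BOP: "BOP was computed to provide a mean score per mouth for each clinical assessment and were analyzed using repeated measures (ANOVA". No group or group-by-visit term is named.
- The next sentence describes between- and within-treatment comparisons of PD and CAL only. BOP is not mentioned.
- A general sentence follows: "Between-treatment and within-treatment comparisons employed baseline data and analysis of covariance (ANCOVA) for follow-up data". It names no outcome.
- All tests are two-sided at 0.05.

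**Abstract.** BOP is among the main outcomes: "relative attachment level (RAL), and changes in bleeding (BOP) using ANCOVA of main effects".

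**Introduction (Chapter One).** The BOP null hypothesis is that the treatment groups do not differ. The primary objectives are benefit over SRP alone across six months and less inflammation before SRP. The secondary objective compares the two durations of gel use.

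**Results (Chapter Three).** Arm means are given at four visits. The starting values are unequal: "Baseline mean BOP was 45% for SRP, 57% for HP13, and 63.1% for HP26". The last values, from week 26, read: "Final mean BOP scores were 44% for SRP, 33% for HP13, and 28% for HP13". That sentence uses the HP13 label twice. One statement of significance follows: BOP fell in every group from the 4-week visit to re-evaluation. The text then describes final BOP as close to re-evaluation in the HP arms and close to baseline in the SRP arm.

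**Discussion (Chapter Four).** After introducing the trial as a comparison with SRP, it calls the gel regimen with SRP statistically significant for BOP reduction.

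**The concern.** The hypothesis is between-arm, so the analysis has to yield a between-arm contrast. A significant fall within every arm, control included, cannot show that gel adds anything to SRP.

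The plan leaves open which model supplies that contrast. Repeated-measures ANOVA with an unnamed treatment term and baseline-adjusted ANCOVA estimate different quantities when baselines differ, and here they differ by up to 18.1 points. BOP is also the only outcome for which the Discussion claims statistical significance for the regimen. A reader cannot tell which contrast, if any, that claim rests on, how large it is, or how precisely it is estimated.

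**Working it through.** The documents give no BOP test statistic, p-value, SD or interval, so there is no figure to reproduce. What can be done is to see what the stated means imply under each candidate method.

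**Inputs** (Results; the second final HP13 value is read as HP26, an assumption):

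| Mean BOP, % | Week 0 | Week 4 | Week 13 | Week 26 | Completers |
|---|---|---|---|---|---|
| SRP | 45 | 45 | 37 | 44 | 3 |
| HP13 | 57 | 60 | 30 | 33 | 3 |
| HP26 | 63.1 | 44 | 27 | 28 | 9 |

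**1. The reported significant interval.** Week 4 to week 13: SRP 37 − 45 = −8; HP13 30 − 60 = −30; HP26 27 − 44 = −17. All three are described as significant, so the statement does not separate the arms.

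**2. Week-26 contrast by method.** ANCOVA estimate = final difference − b × baseline difference, where b is the slope on baseline. No slope is reported, so the full range 0 to 1 is shown. A slope of 0 is the raw final difference. A slope of 1 is the difference in change, which is the baseline-to-final group-by-time contrast.

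| Contrast | Final difference | Baseline difference | b = 0 | b = 0.5 | b = 1 |
|---|---|---|---|---|---|
| HP26 − SRP | 28 − 44 = −16 | 63.1 − 45 = 18.1 | −16.0 | −25.1 | −34.1 |
| HP13 − SRP | 33 − 44 = −11 | 57 − 45 = 12 | −11.0 | −17.0 | −23.0 |
| HP26 − HP13 | 28 − 33 = −5 | 63.1 − 57 = 6.1 | −5.0 | −8.1 | −11.1 |

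The sign is the same throughout. The size roughly doubles from one end to the other.

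**3. Precision.** With 15 completers, three arms and one covariate, residual df = 15 − 3 − 1 = 11 and t = 2.201. The minimum 95% half-width in residual SDs, ignoring the extra term for baseline imbalance, is:
- HP26 vs SRP, and HP26 vs HP13: 2.201 × √(1/9 + 1/3) = 1.467
- HP13 vs SRP: 2.201 × √(1/3 + 1/3) = 1.797

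So the interval for HP26 vs SRP would reach zero at a residual SD between 16/1.467 = 10.9 and 34.1/1.467 = 23.2 points, depending on the slope. For HP13 vs SRP the range is 11/1.797 = 6.1 to 23/1.797 = 12.8 points. Whether the actual SD is above or below these values is not known from the documents.

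**4. A check that needs no assumed SD.** Both HP arms followed the same regimen up to week 13. From baseline to week 4, HP13 changed by 60 − 57 = +3 and HP26 by 44 − 63.1 = −19.1, a gap of 22.1 points between arms treated alike. That is about as large as the treatment contrasts in step 2.

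**The case against.** **The two methods may be complementary.** Repeated-measures ANOVA could describe change over visits, with the general ANCOVA sentence covering between-arm tests of all primary outcomes, BOP included. That would agree with the Abstract. This stands in part: the text shows an ambiguity, not a proven contradiction. But the sentence just before it names only PD and CAL, and on this reading BOP still has two methods, with no statement of which one tests treatment and no reported contrast.

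**The Results do separate the arms at week 26.** Change from baseline is −1 in SRP, −24 in HP13 and −35.1 in HP26, and the text notes that the HP arms held their level while SRP returned near baseline. This stands as description. It is not a test.

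**The Discussion may mean within-arm change.** It does not say greater than SRP. If so, SRP alone also showed a significant fall, and the sentence should say that.

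A reader might be tempted by stronger conclusions that the documents do not support:
- *That no between-arm test was run.* Figures 9 to 11 are not available here and may carry between-arm markings.
- *That the gel has no effect on BOP, or that the method decides the direction.* Averaging all four visits gives 42.75 (SRP), 45.0 (HP13) and 40.525 (HP26), so differences from SRP of only +2.25 and −2.2. But the outcome is framed as reduction or change, so a four-visit average that includes the pre-treatment visit is an unlikely reading.
- *That the pocket-depth subsets settle it.* Neither subset is planned in the Statistical Analysis section, and they point to different sizes. The HP26 − SRP change contrast is (22 − 52) − (33 − 24) = −39 in pockets under 5 mm, while HP13 − SRP is (79 − 81) − (88 − 92) = +2 in those of 5 mm or more.
- *That the SRP week-4 BOP value is invalid.* The SRP schedule lists no data collection then, but week-4 SRP values are also reported for PD, recession and attachment level. This is a schedule discrepancy for every outcome, not a defect of the BOP analysis.

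**Conclusion.** The point holds and should be fixed. The textual findings are firm: two named methods for BOP, no stated treatment term, two roles for one outcome, a between-group hypothesis, and no between-arm BOP contrast in the readable results. As a claim of benefit over SRP, the Discussion sentence is unsupported in the text that can be read. That is the limit of the criticism.

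The size is conditional. The means favour both HP arms at week 26, by 16.0 to 34.1 points (HP26) and 11.0 to 23.0 points (HP13) relative to SRP. This assumes that the relabelled final value belongs to HP26 and that the slope lies between 0 and 1. With three SRP completers and no reported SD, the intervals will be wide. Whether they exclude zero cannot be determined from the documents.

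**What to change.** 1. Name one between-arm BOP analysis: per-mouth BOP at week 26, ANCOVA with baseline BOP as covariate, patient as unit. Report HP13 vs SRP, HP26 vs SRP and HP26 vs HP13 (the secondary objective) with 95% confidence intervals. Label it a post hoc addendum. Because there are three contrasts and three primary outcomes, do not declare significance from unadjusted intervals.
2. For the pre-SRP objective, compare the two HP arms pooled with SRP at week 4, since both followed the same regimen until week 13. First confirm where the SRP week-4 values came from and reconcile the Study Schedule.
3. List BOP once, and align the Abstract and Statistical Analysis with the method actually run.
4. State how sites excluded after re-treatment (Follow Up Care) enter week-26 BOP.
5. Correct or confirm the repeated HP13 label in the Results.
6. Base the Discussion sentence on the between-arm contrast and its interval, or restrict it to a within-arm change that SRP alone also showed.

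**Cost.** Wording in the Abstract, Statistical Analysis, Study Schedule, Results and Discussion, an addendum, and ANCOVA fits to data already collected; no new patients or visits. The downsides are real. The arm means are already known, the covariate uses one of few degrees of freedom, and for slopes below 1 ANCOVA gives a smaller apparent benefit than the change contrast. With three SRP completers the analysis may not settle the claim. Naming the group-by-time term would also remove the ambiguity; ANCOVA is preferred because baselines differ and the Abstract already names it.
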